8. PRIVACY AND CONFIDENTIALITY

All participant information and specimens are handled in compliance with the Health Insurance Portability and Accountability Act (HIPAA) and privacy policies of Stanford University, Stanford Health Care, and Stanford Children's Health.

Perioperative Oral Steroids for Chronic Rhinosinusitis Without Polyps

Statistical Analysis Plan

NCT02748070

July 2, 2020

[name], Principal Investigator
Stanford University
Stanford, California 94305

The planned sample size was 75 patients. By power analysis, we required 50 patients to achieve statistical significance. We collected outcome measures of SNOT-22 and Lund-Kennedy endoscopy scores at the following time points: preoperative baseline, and postoperatively at 1 week, 1 month, 3 months, and 6 months.

All statistical analyses were performed using Stata 15 (Stata Statistical Software: Release 15; StataCorp LP, College Station, Texas). SNOT-22 total scores, SNOT-22 subdomain scores, Lund-Kennedy endoscopic scores, and adverse effects were compared between prednisone and placebo groups at each time point using t-tests.

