2. STUDY PROCEDURES

a. Procedures

Screening: Patients who have been recommended to undergo endoscopic sinus surgery by our department will be recruited for the study and informed of its purpose pre-operatively. SNOT22 scores (a quality of life survey well established in Rhinology) and Lund-Kennedy endoscopic exam scores (an quantitative clinical assessment of disease severity) will be recorded in their medical records. This is the same protocol performed for all patients seen in our clinic regardless of their enrollment in the study. Randomization and Treatment Groups: The patients that wish to participate will be randomized into two treatment arms by our nurse practitioner based on a random number generator. They will receive one of the following post-operative regimens: 1) oral steroid (treatment) + steroid spray (treatment) 2) oral placebo (control) + steroid spray (treatment) These medications will be manufactured and packaged by an independent compounding pharmacy, and prescribed by our nurse practitioner at the preoperative visit. Patients will begin their therapy on the first post-operative day. All oral steroid regimens will be given in our institution's standard 12 days taper, while topical steroids will be delivered via a metered dose nasal spray bottle for two weeks. All study patients will receive identical perioperative antibiotic therapy. We do not anticipate these medications to be an inconvenience to study patients as all proposed interventions are not different from routine post-operative care. In addition, patients undergoing surgery will have already trialed these medications as part of their pre-operative medical therapy. Surgery: Routine endoscopic sinus surgery will be performed per our institution's standard protocol. In this step there will be no difference in treatment from those patients not enrolled in the study. Post-Operative Care: At this point, patients will begin therapies according to the treatment arm to which they have been randomized. Study patients will attend post-operative appointments at identical time points to non-study patients. These will take place at the following intervals: Post-operative visit 1: 1-2 weeks Post-operative visit 2: 6-8 weeks Post-operative visit 3: 12-16 weeks Post-operative visit 4: 6 months Experimental therapy will finish after 2 weeks. At this visit, all patients will then be maintained on intranasal steroid spray and nasal saline irrigations, which is the commonly employed therapeutic standard. Thereafter, patients will, per standard protocol, be followed on an observational basis depending on the severity of symptoms and response to treatment. At each visit, as is done for all individuals, SNOT-22 and LundKennedy endoscopic exam scores will be repeated and recorded.

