6. RISKS

a. Potential Risks

i. Investigational devices

NA

ii. Investigational drugs

NA

iii. Commercially available drugs, biologics, reagents or chemicals

Oral Prednisone: The side effects of short courses of systemic steroids (<3 weeks) include stomach upset, weight gain, insomnia, hyperglycemia, hypokalemia, adrenal suppression, and mood changes. These can occur in up to 16% of patients, with stomach upset being the most common. These effects are all reversible after stopping the steroid. Topical Fluticasone: The side effects of topical steroids include dry throat, sore throat, nasal irritation, headache, nose bleeds. These are the more common side effects, the incidence of which is unknown. Rare and serious side effects include difficulty breathing, flu symptoms, and vision changes. Again, these typically improve after stopping the steroids. On very rare occasion, vision symptoms may be permanent. None of these interventions differ from those already being instituted by our staff.

iv. Procedures

See the risks of the commercially available drugs - None of these interventions differ from those already being instituted by our staff.

v. Radioisotopes/radiation-producing machines

NA

vi. Physical well-being

NA

vii. Psychological well-being

NA

viii. Economic well-being

NA

ix. Social well-being

NA

x. Overall evaluation of risk

Low - innocuous procedures such as phlebotomy, urine or stool collection, no therapeutic agent, or safe therapeutic agent such as the use of an FDA approved drug or device.

b. International Research Risk Procedures

NA

c. Procedures to Minimize Risk

Medication administration will be monitored during the post-operative visits. Patients will begin their assigned therapy the day after surgery, and then will be seen 1, 2, and 4 weeks post-operatively. Any side effects being encountered will be discussed at these visits, and specialty services available in a timely manner to address them if needed. Furthermore, patients have 24 hour access to a physician in the department, and are, at any time, able to call with questions or concerns regarding their treatment.

Identifiable patient information will be handled per institutional protocol. Unique login information is required for all persons wishing to access the electronic medical system. All communications with patient data are sent on a secured machine via an encrypted service that is password protected.

d. Study Conclusion

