7. BENEFITS

The current standard of care in the management of CRS patients with and without nasal polyposis after endoscopic sinus surgery involves a non-standardized regimen of antibiotics and systemic steroids. However, the use of oral steroids in this period is based on anecdotal evidence and expert opinion (level IV evidence). Given the known risks of oral steroid use, it is important to definitively establish their utility and to investigate alternatives. Our study first seeks to more clearly define the role of steroids, both oral and topical, in the perioperative setting. Furthermore, we intend to establish topical steroids as a safer but equally effective therapy. This information will be invaluable to the field and practice of Rhinology. There is a great need for additional investigation to determine whether steroids truly have a beneficial role in post-operative CRS patients. We endeavor to provide randomized, controlled data on which clinicians may base their therapeutic decisions. In addition, the introduction of topical steroids into routine post-operative care would fundamentally change current clinical practices, and may even influence future guidelines. For patients, this may transform their post-operative care into one that is more easily tolerated with less detrimental effects on health.

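### Adverse effects, most naturally yes/no per patient, are compared by t-test at each visit, with no defined coding or exposure window and no usable result when neither arm has an event

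*SAP*

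**What the plan says.** The SAP's single analysis sentence names SNOT-22 total and subdomain scores and Lund-Kennedy scores, then continues: "and adverse effects were compared between prednisone and placebo groups at each time point using t-tests". The sentence that sets out the visits reads "We collected outcome measures of SNOT-22 and Lund-Kennedy endoscopy scores at the following time points", followed by "preoperative baseline, and postoperatively at 1 week, 1 month, 3 months, and 6 months". That list is introduced for the two scores. Adverse effects are not mentioned in it.

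Protocol section 6a.iii says of short-course oral prednisone effects: "These can occur in up to 16% of patients, with stomach upset being the most common". Section 6c has side effects discussed at the post-operative visits. Section 2a starts study drug on the first day after surgery, gives the oral taper as 12 days, and ends experimental therapy at 2 weeks.

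Neither document says whether an adverse effect is a yes/no indicator, a count or a severity score. Neither gives an observation window, a risk difference, a confidence interval or any other test for adverse effects.

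**The concern.** A t-test compares means of a roughly continuous measure. Effects such as stomach upset, insomnia or hyperglycemia, reported as a percentage of patients, are proportions. With 25 to 37 patients per arm and low rates, the number of events may be very small or zero.

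Safety matters to the trial's argument. Section 7 of the protocol states: "we intend to establish topical steroids as a safer but equally effective therapy". The t-test sentence is the whole statistical plan for the first half of that claim. If it gives no answer for some effects, a borderline answer for others, and includes visits long after exposure, the safety conclusion is weaker than the data could support.

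**Working it through.** **Inputs from the documents.** The SAP gives two sizes: "The planned sample size was 75 patients" and "By power analysis, we required 50 patients to achieve statistical significance". Protocol section 2a has patients "randomized into two treatment arms by our nurse practitioner based on a random number generator", with no allocation ratio. The only event rate is up to 16% on oral steroid.

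**Assumptions.** Allocation is 1:1, so 25 per arm (50 in total) or 37 per arm (74 of the 75). Tests are two-sided at 0.05. Placebo rates, and all rates below 16%, are a range chosen for the check.

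**The plan's own figure.** The documents give no calculation for adverse effects. The 50 cannot be reproduced, because no endpoint, effect size, SD, alpha or power is stated.

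**1. No events in either arm.** Both variances are zero and t is undefined. With rate p in both arms and n per arm, the probability is (1 − p)^(2n). At p = 2%:
- 25 per arm: 0.98^50 = 0.364
- 37 per arm: 0.98^74 = 0.224

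**2. Borderline tables.** On 0/1 data the pooled variance is s² = [n₁p₁(1−p₁) + n₂p₂(1−p₂)]/(n₁+n₂−2), and t = (p₁−p₂)/√[s²(1/n₁+1/n₂)]. Both examples put the oral-steroid arm at about the protocol's 16%.
- 6/37 v 1/37: s² = (5.027 + 0.973)/72 = 0.0833; SE = √(0.0833 × 2/37) = 0.0671; t = 0.1351/0.0671 = 2.01.
- 4/25 v 0/25: s² = 3.36/48 = 0.070; SE = √(0.070 × 2/25) = 0.0748; t = 0.16/0.0748 = 2.14.

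| Table | t-test p | Boschloo p | Fisher p | 95% t interval | 95% Newcombe interval |
|---|---|---|---|---|---|
| 6/37 v 1/37 | 0.048 | 0.081 | 0.107 | 0.1% to 26.9% | −0.5% to 28.6% |
| 4/25 v 0/25 | 0.038 | 0.065 | 0.110 | 1.0% to 31.0% | −0.4% to 34.7% |

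Boschloo is computed with the arm sizes as the fixed margin. Fisher is known to be conservative, so Boschloo is the fairer comparator. Both disagree with t here.

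**3. False-positive rate with equal rates (exact enumeration of two binomials).**

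| True rate in both arms | 25 per arm | 37 per arm |
|---|---|---|
| 1% | 0.02% | 0.07% |
| 2% | 0.2% | 0.6% |
| 5% | 2.0% | 3.9% |
| 16% | 5.5% | 5.2% |

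The peak at 37 per arm is about 5.8%, near a 10% rate.

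**4. Coverage of the nominal 95% interval that accompanies the t-test.**

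| True rates | 25 per arm | 37 per arm |
|---|---|---|
| 16% v 2% | 91.6% | 93.2% |
| 16% v 5% | 94.9% | 94.8% |
| 16% v 8% | 94.5% | 94.9% |
| 16% v 10% | 94.5% | 94.9% |

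At 16% v 2%, most misses lie below the true difference, so they understate harm. Newcombe covers 97.4% (25 per arm) and 96.6% (37 per arm) in that case.

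**5. Timing.** Set against the SAP's visit list, 1 week falls within the 12-day taper, while 1, 3 and 6 months fall after therapy ends at 2 weeks. The preoperative baseline precedes any study drug.

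**The case against.** Several stronger readings are tempting, and the documents do not support them.

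- **Rare events produce false signals.** A reader might infer this from the tables in step 2. Step 3 shows otherwise: the t-test's false-positive rate is below 5% for rates of 5% or less, and at most about 6% near 10%. The disagreement with exact tests is confined to a narrow band of borderline tables.
- **The t interval fails badly at low rates.** At 5% v 1% and 25 per arm its coverage is 77.6%. But 0.95^25 × 0.99^25 = 21.6% of trials have no event in either arm, and these are nearly all of the misses. Without them coverage is 0.776/(1 − 0.216) = 99%. This is the defect of step 1 again and should not be counted twice. The shortfall at 16% v 2% does survive: without the no-event trials, coverage is still 92.3% and 93.3%.
- **The plan's safety intervals are wrong.** The SAP specifies no interval. The coverage figures describe only what the t-test would supply if one were reported.
- **Adverse effects are tested at baseline.** This is one literal reading of a compressed sentence. The visit list belongs to the two scores, and the protocol has side effects discussed at post-operative visits.

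It is also fair to say that a placebo rate of 2% may be too low. Both arms have surgery, antibiotics and steroid spray, and at placebo rates of 5% to 10% coverage is close to nominal. Yes/no coding is itself an inference. Finally, protocol section 2g names symptom and endoscopy scores as the outcomes, not adverse effects.

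These objections limit the size of the point. They do not supply a definition, a window or a method that works when events are absent. If counts or severity scores were intended, the SAP still has to say so.

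**Conclusion.** The point holds as a modest analysis defect. The SAP applies a t-test to what are most naturally proportions. The test gives no result for 0 v 0 (36% or 22% of trials at an assumed 2% rate in both arms), and it crosses 0.05 in borderline tables where Boschloo and Fisher do not. Any interval taken from it would under-cover by about 2 to 3 points at an assumed 16% v 2%, and would be near nominal at 16% v 5% to 10%. Neither document states which visits or window carry the safety comparison. On the literal wording it includes three visits after experimental therapy ends, and possibly the baseline.

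There is no general excess of false positives for rare events, and the SNOT-22 and Lund-Kennedy comparisons are untouched. The figures rest on 1:1 allocation, yes/no coding and assumed rates. Only the upper figure of 16% on oral steroid comes from the documents.

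**What to change.** Remove adverse effects from the t-test sentence in the SAP and add a separate statement along these lines:

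- Each adverse effect is coded yes/no per patient.
- The comparison covers first dose to the first visit after the oral taper.
- The number of patients with at least one adverse effect, and with each steroid-type effect, is compared between arms as a risk difference with a 95% Newcombe or Miettinen-Nurminen interval and one named exact test (Fisher or Boschloo).
- Effects recorded at other visits are listed by arm without tests.

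The SAP should name the visit that closes the window. The SAP lists 1 week and then 1 month, while protocol section 6c lists 1, 2 and 4 weeks, so the schedules need to be reconciled first.

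The cost is a few lines of SAP text and code. It should need no new data, provided effects were recorded by visit, as the existing per-visit comparison presupposes. The downside is that some borderline p-values become less favourable.

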
b. Procedure Risks

This study does not seek to evaluate a novel research procedure. Rather, we endeavor to determine if a procedure already in place nearly universally is, in fact, beneficial, as there is a

distinct lack of evidence of suggest so. Overall, we are investigating a procedural method that will have fewer side effects than the currently accepted practice.

c. Use of Deception in the Study

NA

d. Use of Audio and Video Recordings

NA

e. Alternative Procedures or Courses of Treatment

All reasonable alternatives are included as a treatment arm in this study. There is no standard of care that is being withheld from patients in any group.

f. Will it be possible to continue the more (most) appropriate therapy for the participant(s) after the conclusion of the study?

Yes, patients will stop all experimental therapies at the 2 week mark. They will then be placed on the typical post-operative regimen, which includes a nasal steroid spray and twice daily saline irrigations. They will continue to be followed in our clinic after the 4 week mark, and their therapies tailored to their current symptoms and the endoscopic appearance of the nasal cavity.

g. Study Endpoint(s)

Currently, our post-operative protocol dictates that patients will be seen in clinic at 1 week, 3 weeks, and 6 weeks after surgery. We will only slightly alter this timeline for study patients. At the 2 week appointment, all experimental therapies will be completed. Patients will then be started on intranasal steroid sprays and saline irrigations so as not to deviate for an extended period from currently accepted practices. We will use the final scheduled appointment at 4 weeks after surgery as the official end point for comparison of treatment arms. Additionally, outcomes evaluated will be the symptom questionnaire and the endoscopic exam score at each visit. If, during the course of follow up, one regimen proves to be clearly superior to another, the study will be terminated and patients will receive the optimal therapy. By power analysis, we require 50 patients to achieve statistical significance. If there is a clearly optimal therapy determined in these first 50 patients, we will end our research at that time. All patients will continue to be followed beyond 4 weeks depending on symptom severity and response to treatment

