support its use (1). Therefore, this almost universal current practice is perpetuated by anecdotal data and expert opinion. Furthermore, systemic steroids are associated with known significant side effects and potential drug interactions. These may be severe and include but are not limited to high blood pressure, hyperglycemia and diabetes, adrenal suppression, weight gain, glaucoma, osteoporosis, fluid retention, gastrointestinal bleeding, ulcers, and mood changes (2). Thus, oral steroids potentially pose a significant risk, have unproven benefit, and are not appropriate for repeated or longterm use – an unfortunate obstacle in treating a chronic disease. Recently, steroids dissolved in a saline irrigant have been increasingly used and proven to be effective in the routine management of CRS. Furthermore, several studies have suggested the utility and safe side effect profile of these medications; however, the data supporting their use as a perioperative treatment is distinctly lacking. While the data to support the utility of topical steroids in the treatment of CRS is evident, relatively few groups have explored topical steroid irrigations specifically as a peri-operative intervention. Fandino et al conducted a meta-analysis of 13 randomized clinical trails and cohort studies examining the use of topical steroids delivered via drops, sprays, nebulizers, or irrigations for patients with CRS with nasal polyps who had previously undergone endoscopic sinus surgery. According to his analysis, intra-nasal corticosteroids had a significant beneficial effect on symptom scores and a reduction in polyp scores. Additionally, the use of INCS decreased the rate of polyp recurrence, and did not alter adrenocorticotrophic hormones post-intervention, suggesting the intra-nasal delivery method to carry less risk than the oral version (3). Snidvongs et al conducted a study with 111 patients and reported significant improvement in symptom scores and endoscopy scores over those who did not receive postoperative topical steroids (4). Jang et al retrospectively evaluated 60 patients postsurgically who were treated with topical steroid deliveries and showed a significant decrease in quality of life and endoscopy scores after patients stopped their treatments (5). In summary, the data supporting the use of steroids in patients with CRS immediately after endoscopic sinus surgery is sparse. We, therefore, seek to more definitively elucidate the role and utility of steroid treatment in the peri-operative period. Furthermore, per our review of the literature, there has been no direct comparison of the traditional oral regimen to topical therapy (nasal spray). Could these be proven equally effective, topically delivered steroids may be considered as a replacement for systemic steroids. This would represent a significant shift and improvement in the current post-operative management of CRS. Patients would avoid the innumerable side effects of oral steroids, which are detailed above. Furthermore, while oral steroid usage is often limited by unwanted side effects, a topical regimen may be sustained over a prolonged period as a maintenance therapy if symptoms necessitate.

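### The SAP tests adverse effects only visit by visit and plans no per-patient comparison over the 12-day prednisone course

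*SAP*

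**What the plan says.** The SAP gives adverse effects one clause: "adverse effects were compared between prednisone and placebo groups at each time point using t-tests". The only time points it names are "preoperative baseline, and postoperatively at 1 week, 1 month, 3 months, and 6 months", and it names them for SNOT-22 and the Lund-Kennedy score. Reading them across to adverse effects is natural, since one sentence covers all the outcomes. The SAP states no recall window, no scale (yes/no, count or severity) and no analysis that pools visits.

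The protocol fixes the exposure. Section 2a says "Patients will begin their therapy on the first post-operative day" and "All oral steroid regimens will be given in our institution's standard 12 days taper", so the last dose falls on about day 12.

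The protocol's visit schedule is less clear:
- Section 2a lists "Post-operative visit 1: 1-2 weeks Post-operative visit 2: 6-8 weeks", followed by visits at 12 to 16 weeks and 6 months. It then says "Experimental therapy will finish after 2 weeks. At this visit, all patients will then be maintained on intranasal steroid spray".
- Section 2g says "At the 2 week appointment, all experimental therapies will be completed".
- Section 6c puts visits at 1, 2 and 4 weeks and has side effects discussed at them.

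Section 6e lists adverse events for safety review, but neither document plans a between-arm comparison over the course.

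**The concern.** Steroid harm is part of the reason for the trial. Section 3a says that "oral steroids potentially pose a significant risk, have unproven benefit", and section 7 hopes to show topical treatment to be the safer option. A clinician would want to know how many more patients had a side effect during the course on prednisone than on placebo. Separate tests at each visit do not give that figure. They divide a small number of affected patients by the date of the visit that logged them, and the later visits fall well after a drug whose short-course effects section 6a describes as reversible once it is stopped. The difference seen at any one visit then depends partly on scheduling and recording.

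**Working it through.** **1. Where the time points fall.** The last dose is on day 12. Nominal days since the last dose are:
- 2-week appointment (not a named SAP point): 14 - 12 = 2
- 1 month: 28 - 12 = 16, or 30 - 12 = 18
- 3 months: 84 - 12 = 72, or 90 - 12 = 78
- 6 months: 180 - 12 = 168

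Day 7 is inside the taper, with 12 - 7 = 5 days of tablets still to come.

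**2. Two readings of the 1-week point.**
- *It means day 7.* Days 1-7 belong to the 1-week comparison. Days 8-12 belong, if anywhere, to the 1-month comparison, which also covers at least 16 days off drug.
- *It labels the section 2a visit at 1 to 2 weeks.* That visit falls on days 7-14. Held on days 12-14, it can cover the whole course; held on days 7-11, it covers most of it.

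The SAP's four post-operative points match section 2a's four visits in number and order, which favours the second reading. Against that, the SAP's 1 month does not fit section 2a's 6 to 8 weeks; it fits the 4-week visit in sections 2g and 6c. Neither reading can be established.

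**3. What splitting does to the estimate.** If on-tablet events are recorded at two visits and none is lost, P(any) <= P(visit A) + P(visit B). The larger single-visit proportion is therefore between 50% and 100% of the whole-course proportion.

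For illustration, assume 37 per arm (75/2, rounded down) and the top short-course rate in section 6a: 16% x 37 = 5.9, taken as 6 prednisone patients. The placebo count is not in the documents, so take 2. Assume each affected patient is recorded at one visit only.
- Whole course: 6/37 - 2/37 = 16.2% - 5.4% = 10.8 points, whichever visit logged the events.
- Split 3-3 on prednisone and 1-1 on placebo: each visit shows (3 - 1)/37 = 5.4 points.
- Split 6-0 on prednisone and 0-2 on placebo: one visit shows 6/37 = 16.2 points, the other -2/37 = -5.4.

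The two visit differences always sum to 4/37, so the larger lies between 2/37 (5.4 points) and 6/37 (16.2 points).

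**4. Precision of the whole-course estimate.** The Newcombe interval uses the Wilson limits (l, u) of each arm. The lower limit is d - sqrt[(p1 - l1)^2 + (u2 - p2)^2], and the upper is d + sqrt[(u1 - p1)^2 + (p2 - l2)^2]. Equal arms are assumed throughout.

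| Assumed patients affected | Difference (points) | 95% CI |
|---|---|---|
| 6 v 2, 37 per arm | 10.8 | -4.2 to 26.2 |
| 6 v 1, 37 per arm | 13.5 | -0.5 to 28.6 |
| 6 v 0, 37 per arm | 16.2 | 3.5 to 31.1 |
| 4 v 0, 25 per arm | 16.0 | -0.4 to 34.7 |

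Only 6 v 0 at 37 per arm excludes zero, and it rests on an assumed empty placebo count.

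**5. Does the choice of test matter?** Exact power was found by summing binomial probabilities over all outcomes with p < 0.05. The assumptions are 37 per arm, 16% v 5% over the course, and 7/12 of events by week 1, so the week-1 rates are 16% x 7/12 = 9.3% and 5% x 7/12 = 2.9%.
- Week-1 t-test: 0.20
- Whole-course t-test: 0.37
- Whole-course Fisher's exact test: 0.19

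The gain comes from pooling by patient, and moving to Fisher's test gives it back. On yes/no data the t-test's exact false-positive rate at 37 per arm is 0.052 when both arms are at 16%, and 0.039 at 5%. At 25 per arm it is 0.055 and 0.020.

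**The case against.** The strongest reply is that the timing gap may be no more than a label. If the SAP's first point is section 2a's visit at 1 to 2 weeks, which that section seems to treat as the end of therapy, one comparison already covers most or all of the course. The SAP also attaches its time points to the efficacy scores and does not say how adverse effects were recorded. If they were counts or severity scores, a t-test is ordinary and the yes/no illustration does not apply. This stands, and it makes the split conditional. It does not supply the missing analysis: under either reading, no per-patient comparison over the course is planned.

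A reader might infer that late-taper events are lost. The documents do not support that, because the 1-month visit may record events since the previous visit, section 6c places a 2-week visit in the schedule, and patients could reach a physician at any hour. Whether anything is under-counted is unknown.

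A reader might also infer that the t-test is invalid and must give way to Fisher's exact test. The false-positive rates above do not show that, and the exact test would roughly cancel the power gained by pooling. Nor should a significant 6 v 0 result carry the argument, since it is an assumed favourable case.

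**Conclusion.** The point holds in a limited form. The SAP compares adverse effects only by visit and plans no any-event proportion per arm over the 12-day course. How far the course is actually split depends on what the 1-week point means and on the recall window, and the documents give neither.

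The benefit of changing is an interpretable whole-course estimate that does not move with the visit that logged the event. In the 6 v 2 illustration it replaces a larger per-visit difference of anywhere from 5.4 to 16.2 points with a single 10.8. That rests on assumed equal arms, an assumed placebo count, and one recorded visit per affected patient. The estimate will be imprecise whatever is done: its interval there runs from -4.2 to 26.2.

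Adverse effects are not among the endpoints in section 2g, so the efficacy comparison is untouched. This is a worthwhile, inexpensive improvement to a secondary comparison.

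**What to change.** 1. Make the main safety result the proportion of patients in each arm with any adverse effect from the first tablet to the end-of-therapy visit at about 2 weeks, counting each patient once.
2. Report the risk difference with a 95% confidence interval (Newcombe, for example) as the primary summary. Fisher's exact test need not be required.
3. Build it from side effects already recorded at visits and in patient calls during that period, extracted the same way in both arms.
4. State in the SAP which early visits took place, what the 1-week point refers to, and the period each adverse-effect record covers.
5. List events at 1, 3 and 6 months as counts by arm.

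The cost is a few sentences of SAP text and a small amount of record extraction. The SAP is written in the past tense, so new data collection is probably closed; only if it is open should both arms be asked at the 2-week contact about any side effect since the first tablet. With few events the interval will be wide, and records for days 8-12 may be incomplete. If so, the report should say so.

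### SNOT-22 and Lund-Kennedy are measured before surgery, but the SAP's t-tests on postoperative scores do not use the baseline, which probably costs precision

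*SAP*

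**What the plan says.** The SAP is one page. On data collection it states: "We collected outcome measures of SNOT-22 and Lund-Kennedy endoscopy scores at the following time points: preoperative baseline", followed by four postoperative times. Its efficacy analysis is a single sentence: SNOT-22 total and subdomain scores and Lund-Kennedy scores "were compared between prednisone and placebo groups at each time point using t-tests". Adverse effects are in the same sentence but are not at issue here.

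Protocol section 2a has both scores recorded preoperatively for every clinic patient, enrolled or not: "This is the same protocol performed for all patients seen in our clinic regardless of their enrollment in the study". Baseline values should therefore exist for everyone randomised.

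On size, the SAP says: "The planned sample size was 75 patients. By power analysis, we required 50 patients to achieve statistical significance". Neither document gives an effect size, SD, significance level, power or correlation between baseline and follow-up. Neither mentions ANCOVA, change from baseline or a model across visits.

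**The concern.** Scores tested at each time point are, on the plain reading, raw scores. A t-test at the baseline visit would show an imbalance but would not carry the baseline into any postoperative comparison. Patients differ before surgery, and whatever part of that difference persists stays in the error term of the prednisone-placebo comparison.

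The stake is mainly interval width. Protocol sections 3a and 7 hope to show that topical steroid without the oral course works equally well. If the arms look similar, what the trial can conclude depends on how large a difference the interval excludes.

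A chance baseline difference between arms also moves the unadjusted result in the one trial that was run, although it averages to zero over randomisations.

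**Working it through.** **The plan's own figure.** The 50 cannot be reproduced, because none of its inputs is stated. To have a reference effect I assumed two-sided alpha 0.05, 1:1 allocation (25/25) and 80% power for the t-test at N=50. The noncentral t then gives a difference of 0.809 SD. At the same 0.809 SD with 75 patients (38/37), the t-test has 93% power.

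**Inputs.** N=50 and N=75 are from the SAP. The correlation r is assumed, from 0.1 to 0.6.

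**Formulas.**
- Variance of the ANCOVA difference relative to the t-test: (1 − r²) × (1 + 1/(N − 4)). The second factor is the cost of estimating the slope.
- CI width ratio: the square root of that, times t(0.975, N − 3) / t(0.975, N − 2).
- Example, N=50 and r=0.5: 0.75 × (1 + 1/46) = 0.766; √0.766 = 0.875; times 2.0117/2.0106 gives 0.876, so 12% narrower.

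**Results.**

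| r | CI ratio, N=50 | ANCOVA power, N=50 | CI ratio, N=75 | ANCOVA power, N=75 |
|---|---|---|---|---|
| 0.1 | 1.006 | 80% | 1.002 | 93% |
| 0.2 | 0.991 | 81% | 0.987 | 94% |
| 0.3 | 0.965 | 83% | 0.961 | 95% |
| 0.5 | 0.876 | 89% | 0.872 | 98% |
| 0.6 | 0.809 | 93% | 0.806 | 99% |

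The t-test powers to set against these are 80% and 93%. The ratio equals 1 at r = 0.150 (N=50) and r = 0.120 (N=75).

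**Interval width in SD units.** The t-test half-width is t × √(1/n₁ + 1/n₂): 2.011 × 0.283 = 0.57 SD at N=50, and 1.993 × 0.231 = 0.46 SD at N=75. ANCOVA with 50 patients at r=0.6 gives 0.809 × 0.57 = 0.46 SD, the precision of the unadjusted analysis of 75.

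**Chance imbalance.** One standard error of the baseline difference is √(1/25 + 1/25) = 0.283 SD at N=50 and √(1/38 + 1/37) = 0.231 SD at N=75. The unadjusted difference moves by r times that: 0.03 to 0.17 SD at N=50 and 0.02 to 0.14 SD at N=75.

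**Validity check.** In simulation (20,000 trials per setting), type I error was 0.048-0.052 for the t-test and 0.049-0.053 for ANCOVA. Both are valid, and the simulated ANCOVA powers agreed with the table.

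**Why not change scores.** Their variance relative to raw scores is 2(1 − r). At r=0.3 that is 1.4, worse than no adjustment; change scores help only above r=0.5.

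**The case against.** The t-test is valid, so this is a preference for efficiency whose size rests on an unstated correlation. Features of this trial could make r low. Surgery falls between baseline and every follow-up, and Protocol section 5m allows 1 to 6 months or longer between first encounter and operation. One r need not fit both instruments or every visit from 1 week to 6 months. At r=0.3 the gain is only about 4% in width. Power is little affected at the planned size, since under the assumed effect the t-test already has 93% at 75 patients. Imbalance correction and precision gain are also one mechanism, not two harms. Finally, adding results to a SAP written in the past tense invites choosing between them.

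Most of this stands as a limit on weight. The correlation may be low, where materiality begins is a judgement, and the imbalance shift should not be counted as a further loss on top of the width.

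It does not remove the point. The risk is lopsided: at most 0.6% wider at r=0.1 against 19% narrower at r=0.6. The width gain is nearly the same at 75 patients as at 50, even where power is already high. The danger of selection is met by saying which result governs.

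**Conclusion.** The concern holds as a point of efficiency, not validity. The baseline is collected and the specified analysis does not use it. The interval is probably wider than it needs to be: the gain from adjusting is nil or slightly negative at r=0.1, small at r=0.2, about 4% of CI width at r=0.3 and 12-19% at r=0.5 to 0.6. The CI figures rest on the assumed r and roughly equal arms. The power figures also rest on the assumed alpha and on 50 patients giving 80% power. The change should be made, but nothing in the t-test results is invalid without it. Confidence is medium, because r is unknown.

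**What to change.** Keep the t-tests and report the adjusted result next to them. Suggested text:

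> For SNOT-22 total, each SNOT-22 subdomain and Lund-Kennedy, the postoperative score at each visit is regressed on arm and the preoperative value of the same score (ANCOVA). Patients are analysed in the arm to which they were randomised. The adjusted difference is reported with its 95% CI and the number analysed in each arm.

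One mixed model per score, with baseline-by-visit and treatment-by-visit terms, is an acceptable alternative; choose one and say so. State which analysis the conclusion rests on. If results have been seen, label the adjusted analysis as added and leave the t-test as the planned one.

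A main comparison also needs one time point, and the documents disagree. Protocol sections 2g and 6e.iv say "We will use the final scheduled appointment at 4 weeks after surgery as the official end point for comparison of treatment arms". Section 6c says patients "then will be seen 1, 2, and 4 weeks post-operatively". Section 2a gives "Post-operative visit 1: 1-2 weeks Post-operative visit 2: 6-8 weeks", then 12-16 weeks and 6 months. The SAP gives "preoperative baseline, and postoperatively at 1 week, 1 month, 3 months, and 6 months". These passages must be reconciled. That is a separate matter and adds no weight to the baseline point.

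The cost is a re-run on existing data in the Stata 15 already named: one regression per score and visit, with subdomain baselines from the same questionnaire. No new visits or patients are needed.
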